pre-post change in cognitive control or reward processing circuits as primary predictors, while controlling for baseline impulsivity and treatment group. The mediation effect is then estimated by taking the product of the estimates for **path a and b** and using the bootstrap method to obtain standard errors, confidence intervals, and the test for statistical significance.

To test whether treatment effects on cognitive control or reward processing circuits are specific in mediating improvements in impulsivity, we will explore whether treatment-related changes in other neural networks also mediate the effect of treatment on impulsivity. We will first screen these additional neural networks based on a significant effect of treatment on connectivity within these networks. Only networks that show significant change with treatment will be added to the multiple mediation analyses described above. The indirect effects of the cognitive control or reward processing circuits will be tested in the existence of the mediation effects of other neural networks using the bootstrapping method.

Power: Power for detecting the mediation effect depends on the size of the associations between (a) treatment group and changes in cognitive control and reward processing circuits, and (b) changes in cognitive control and reward processing circuits and changes in impulsivity. Based on tabulated recommendations for sample sizes needed to test mediation effects, with a sample size of $n=60$, we have more than 80% power to detect a significant mediation effect with medium effect size of both paths a and b.

Secondary Objective: ADHD patients with baseline MRI anomalies within reward processing circuits will respond to Vyvanse, but not Intuniv, treatment. Conversely, ADHD patients with baseline MRI anomalies that are circumscribed to cognitive control circuits (i.e., reward processing comparable to healthy controls) will predict response to either Intuniv or Vyvanse.

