We will test the moderation effect of the baseline MRI measures cognitive control and reward processing circuits on the treatment response. We will use linear regression models with pre-post change scores in impulsivity measures as outcomes and Group, baseline measures of cognitive control and reward processing circuits measured in predefined regions of interest (ROIs), and their interactions as predictors. Likelihood ratio tests will be used to test the effect of moderation with combination of multiple brain imaging measures.

Power: With sample size of $n=60$, the minimum detectable effect size of Cohen's f^2 is 0.09 (smaller than medium effect size 0.15) with 80% power for a two-sided test at the 5% significance level. If the effect size of interactions between baseline measures within cognitive control and reward processing circuits and Group is greater than f^2 is 0.09, we would be able to detect such effect size.

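### The secondary analysis names only a Group-by-baseline moderation test, which cannot support the claim that cognitive-control anomalies predict response to both drugs

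*SAP*

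**What the plan says.** The SAP's Secondary Objective has two halves. Children with reward-circuit anomalies "will respond to Vyvanse, but not Intuniv, treatment". Anomalies confined to cognitive-control circuits, with reward measures like those of healthy children, "will predict response to either Intuniv or Vyvanse".

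The analysis paragraph that follows serves both halves. It opens: "We will test the moderation effect of the baseline MRI measures cognitive control and reward processing circuits on the treatment response". It specifies "linear regression models with pre-post change scores in impulsivity measures as outcomes", with treatment group and the baseline circuit measures "measured in predefined regions of interest (ROIs), and their interactions as predictors". The one inferential procedure it names is this: "Likelihood ratio tests will be used to test the effect of moderation with combination of multiple brain imaging measures".

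The power statement reads "With sample size of $n=60$, the minimum detectable effect size of Cohen's f^2 is 0.09", "with 80% power for a two-sided test at the 5% significance level", and it applies that figure to interactions of the baseline measures with Group. The SAP gives no test, decision rule or power for the cognitive-control slope within an arm or averaged over arms. It sets no margin for calling two slopes similar.

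**The concern.** The two halves need different evidence. The reward claim is a difference between arms, which a Group-by-baseline interaction tests. The cognitive-control claim is an association that must exist in the LDX arm and also in the GXR arm. An interaction test compares the two slopes and is silent on whether either differs from zero.

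A non-significant Group-by-cognitive-control interaction fits three situations: the marker predicts response to both drugs, it predicts response to neither, or it predicts response to one and the difference was missed. As written, the plan can produce evidence against equal prediction but has no prespecified route to evidence for prediction in both arms.

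**Working it through.** **Inputs from the documents.** SAP, Secondary Objective: n=60, f²=0.09, 80% power, two-sided 5%, and the model terms. Protocol, Randomization Procedures: 1:1 allocation. Protocol, Lay Summary and Description of Subject Population: 30 children with ADHD, used here as a sensitivity case.

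**Assumptions.** Baseline measures are standardised, the residual SD is 1, and the correlation between the two circuits runs from 0 to 0.5. Slopes are in residual SD per SD of the marker. The documents give no slope, so several are shown. Simulations fit Group, both circuits and both Group interactions. Repeat runs agree to within about two percentage points.

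**1. The plan's own figure.** For one interaction term, the normal approximation gives a minimum detectable f² of (1.960 + 0.842)²/60 = 7.85/60 = 0.131. The noncentral F with λ = n·f² gives 0.136. The stated 0.09 does not reproduce. At f²=0.09, λ = 60 × 0.09 = 5.4 and power is about 63%. This is a separate matter, used here only for the miss rate of about 37%. With 30 children, λ = 2.7 and the miss rate is 65%.

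**2. What the interaction test can see.** Let the cognitive-control slopes be βL (LDX) and βG (GXR). The tested coefficient is βL − βG. It is 0 when both slopes are 0 and also when both are 0.5, so the chance of non-significance is 1 − 0.05 = 0.95 either way. Simulated rates of a non-significant interaction:

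| Slope in both arms | F/t, n=60 | Chi-square LRT, n=60 | F/t, n=30 | Chi-square LRT, n=30 |
|---|---|---|---|---|
| 0 | 95.0% | 93.8% | 95.1% | 91.7% |
| 0.39 (f²=0.15) | 94.7% | 93.3% | 95.2% | 92.0% |
| 0.59 (f²=0.35) | 95.3% | 93.9% | 95.0% | 91.4% |

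A joint likelihood ratio test of both circuits behaves the same way. If the reward measure has an assumed slope of 0.6 in the LDX arm only, the joint test is non-significant in 45.9% of trials at n=60 when cognitive control predicts nothing, and in 47.4% when it has a slope of 0.39 in both arms.

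**3. A marker that works for one drug.** With equal arms and uncorrelated circuits, f² = (βL − βG)²/4. Slope differences of 0.5, 0.6 and 0.7 give 0.0625, 0.09 and 0.1225. Share of trials in which the difference is missed (ranges cover circuit correlation 0 to 0.5):

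| True effect | n=60 | n=30 |
|---|---|---|
| 0.5 vs 0 | 58–66% | 79–82% |
| 0.7 vs 0 | 30–43% | 64–70% |
| f²=0.09 (noncentral F) | 37% | 65% |

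The mean 95% half-width for the slope difference is 0.55–0.64 at n=60 and 0.86–0.99 at n=30. An estimated difference near zero would therefore usually leave a true difference of 0.5 open.

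**4. Testing the claim directly.** Require a significant slope of the same sign in each arm. At a shared slope of 0.39, n=60 and uncorrelated circuits, the arm-level powers are 0.504 and 0.511. Their product, 0.504 × 0.511 = 0.258, matches the simulated joint power. Power of the both-arms rule in the additive model:

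| Shared slope | n=60 | n=30 |
|---|---|---|
| 0.39 | 18–27% | 6–8% |
| 0.5 | 37–51% | 11–18% |
| 0.7 | 75–87% | 30–43% |

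False support is about 0.2% when the marker predicts neither drug and 1–2% when it predicts one (slope 0.5). For a shared slope of 0.5, the slope averaged over arms has power of 87–94% at n=60 and 52–63% at n=30.

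**5. The normal-reward condition.** Those false-support rates assume additivity. Suppose instead that cognitive control has a slope of 1.0 only in children with above-average reward abnormality and 0 in the rest. It then predicts nothing in the children the objective describes. The additive both-arms rule still gives support in about 37% of trials at n=60 (correlation 0) or 27–28% (correlation 0.5). The slope has to be evaluated at normal reward.

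**The case against.** - **The slopes are already in the planned model.** True: the baseline measures are predictors, so both arm slopes can be estimated from the same fit. But with a Group interaction present and 0/1 coding, the printed cognitive-control coefficient is the slope in the reference arm only. Testing the claim needs named contrasts, and none are named.
- **The objective concerns a joint profile, not a cognitive-control slope.** This stands, and it shapes the remedy. The SAP does not say how children with normal reward enter the model. One reading of its interaction wording includes cognitive control by reward.
- **95% is not the figure for the named test.** Correct. It belongs to an F or t test of one coefficient. The chi-square version gives about 94% or 92%, and a joint test gives less if the reward effect is real. In every version the rate is the same whether the marker predicts both drugs or neither, which is all the argument needs.
- **A reader might infer that the investigators will announce a null interaction as confirmation.** Nothing in the SAP says so. The point is only that no other route to support is specified.
- **A reader might infer that a one-drug marker would usually be missed.** The documents do not support that in general. At n=60 it holds for 0.5 versus 0, but not at f²=0.09 or for 0.7 versus 0.
- **This is half of a secondary objective, and the Protocol's background describes the search for response predictors as exploratory.** That limits the weight of the point. It does not make the named test answer the stated question.

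**Conclusion.** The concern holds. The test named in the SAP cannot support the claim that cognitive-control anomalies predict response to both drugs, because its result has the same distribution whether the marker predicts both equally or neither. That conclusion does not depend on the size of the shared slope or on which of the two sample sizes applies.

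The miss rates for a one-drug marker and the power of the both-arms rule do depend on assumed slopes, residual SD 1 and the assumed circuit correlation, and should be quoted only as ranges. The n=30 figures apply if the Protocol's number of children with ADHD governs; its disagreement with the SAP's n=60 is a separate point. Correction before analysis is worthwhile: it needs no new data and gives this half of the objective a test that matches it.

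**What to change.** In the analysis paragraph of the SAP's Secondary Objective, add the following, all from the planned regression:

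1. Code each circuit measure so that higher means more abnormal relative to healthy controls, and centre reward at the healthy-control mean. Include the cognitive-control × reward and Group × cognitive-control × reward terms, so that the cognitive-control slope is evaluated at normal reward. Fix the coding in advance, because the SAP states no sign for these slopes and the Protocol's Hypothesis 1a gives no direction for connectivity.
2. Estimate that slope in each arm with a 95% CI. Claim prediction of response to either drug only if both slopes are significant in the direction of greater improvement.
3. Report the slope averaged over arms as a weaker, separately labelled claim.
4. Report the Group × cognitive-control coefficient with its 95% CI, and state that a non-significant interaction is not evidence of prediction in both arms.

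**Cost.** SAP wording and a few contrasts, with no additional patients. The downside is low power for the both-arms rule, which the SAP should state as a range over assumed slopes, as in step 4 of the working. The extra terms may lower it further: the model goes from 6 to 8 coefficients, leaving 60 − 8 = 52 or 30 − 8 = 22 residual degrees of freedom. The slope at normal reward will also be imprecise if few children with ADHD have reward measures near the control mean. The trial may often support only the averaged-over-drugs statement.

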Exploratory Aim: To examine the concordance between the Pubertal Development Scale (Petersen et al., 1988) and the Tanner Stages and the acceptability of these measures to participants and their parents/guardians. Parent report will be collected if participants are <11 years, and self report will be collected if participants are 11 years or older.

Description of Subject Population

Sample #1

Specify subject population

Children with ADHD

Number of completers required to accomplish study aims

30

Projected number of subjects who will be enrolled to obtain required number of completers

80

Age range of subject population

6-17 years

Sample #2

Specify subject population

Healthy Control Children

Number of completers required to accomplish study aims

30

Projected number of subjects who will be enrolled to obtain required number of completers

80

Age range of subject population

6-17 years

Gender, Racial and Ethnic Breakdown

In terms of gender, we expect the majority of children with ADHD to be male (approximately 80%), which reflects the fact that ADHD is more common in boys than in girls.

In terms of ethnic breakdown, this sample will represent a wide array of racial and ethnic backgrounds that are representative of both the population in the Washington Heights area and New York City at large (e.g., 60% White, 40% Hispanic/Latino of any race, 20% Black/African American, 5% Asian, 10% other race, 5% two or more races). Additional efforts will be made to diversify the population of participants by advertising in community/neighborhood newspapers throughout New York City and surrounding areas. We will first seek IRB approval prior to releasing these advertisements.

Description of subject population

The subject populations will consist of:

- Children with ADHD
- Healthy control children, who will be matched on age and sex.

Recruitment Procedures

Describe settings where recruitment will occur

Study Recruitment Websites

Participants will be recruited through research study recruitment websites such as RecruitMe and Clinicaltrials.gov.

Flyers and Brochures

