- **For ADHD participants with a history of tic disorder:** Based on the information gathered from the medical history and the psychological assessments during the initial visit(s), the study doctor will carefully weigh the risks and the benefits of LDX treatment with the parent/guardian of the child participant. The decision to randomize the participant or to remove him/her from the study will depend on the study doctor's clinical judgment and the preferences of the parent/guardian. The study doctor will follow the same clinical practice guidelines for evaluating and treating co-occurring ADHD and tic disorder as doctors in the community. If the study doctor and parent/guardian agree that the benefits of potential treatment with LDX outweigh the risks, then the participant will proceed to the randomization procedures outlined below.
- **For female ADHD participants who have had their first period:** Female ADHD participants who have had their first period and who are sexually active will need to: (1) be using contraception prior to beginning treatment, and (2) agree to continue using contraception throughout the course of treatment in order to participate in the study. The study doctor will talk to female participants who have had their first period about ways to prevent pregnancy, the potential risks of the study medications on pregnancy (as part of consent/assent), as well as the limitations of urine pregnancy testing. Participants and their parents/guardians will be advised to notify the researcher immediately should they suspect that the participant is pregnant. If a participant is suspected to be pregnant, we will perform another pregnancy test to determine if she should continue the study. In case of pregnancy, the participant will discontinue the study early and we will provide assistance with obstetrical follow-up.

2. Randomization Procedures

Eligible ADHD participants will be randomized to treatment with LDX or GXR using a 1:1 ratio. Participants, research staff, and the study doctor will NOT be blinded to treatment.

3. Medication Management

Following randomization, participants will be taken through a medication management protocol over the subsequent 6 weeks. This protocol will begin with 4 weeks of medication titration, which will be followed by 2 weeks of medication maintenance. Titration will help the study doctor determine the minimum dose of medication necessary to achieve treatment response.

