- **Titration of GXR:** The treating physician will dose GXR to optimize clinical response. Titration will begin at 1 mg and will advance through the dosage range (1 - 4 mg) to find the best response that provides no more than mild adverse events. Treatment response will be defined as a clinician-rated CGI-I score ≤ 2 (Improved or Very Much Improved) with no more than mild associated adverse events based on a clinical review of side effects. For children under 25 kg/55 lbs, the dose of GXR will not exceed 1 mg per day. The treating clinician will monitor heart rate and blood pressure to ensure that cardiovascular risk is minimized. Flexibility in the dosing will be up to the treating physician as long as the dosing does not go outside of the FDA approved guidelines of 1 - 4 mg daily.

- **Concomitant Medication:** The treating physician will review any potential concomitant medications, and make recommendations as clinically indicated. For example, GXR doses may be adjusted when used concomitantly with strong CYP3A4 inhibitors (e.g., boceprevir, clarithromycin) or inducers (e.g., avasimibe, carbamazepine). In clinical practice, melatonin is often used to alleviate insomnia related to ADHD medications like LDX. The treating physician will have the option of recommending melatonin 1-6 mg nightly as needed for insomnia.

See Criteria for Early Discontinuation

Follow Up Evaluation and MRI Scan

After completing the medication trial, children with ADHD will be scheduled for a follow-up evaluation. The follow-up evaluation will be similar to the baseline evaluation but shorter in length. The second MRI scan will be identical to the first MRI scan.

1. **Neuropsychological Testing:** We will repeat all neuropsychological tests with the exception of the measure of intelligence, which is not expected to change during the study period.
2. **Diagnostic Assessments:** Likewise, we will repeat all diagnostic assessments with the exception of the diagnostic interview.

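### The moderation model leaves out baseline impulsivity, a covariate already collected; adding it would sharpen the Group-by-ROI test at almost no cost

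*SAP*

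**What the plan says.** The moderation model is in the SAP under the Secondary Objective. Its outcome and first predictors are given as "We will use linear regression models with pre-post change scores in impulsivity measures as outcomes and Group, baseline measures of cognitive control"; the reward-circuit measures follow, and the list closes with "measured in predefined regions of interest (ROIs), and their interactions as predictors". No baseline impulsivity term appears. I read Group as treatment arm, since only the children with ADHD are treated and reassessed. The joint test is described as "Likelihood ratio tests will be used to test the effect of moderation with combination of multiple brain imaging measures". The power statement for n=60 says that "the minimum detectable effect size of Cohen's f^2 is 0.09" at 80% power, two-sided 5%.

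The SAP's Primary Objective has a related model. Path b also takes change in impulsivity as its outcome, but is fitted "while controlling for baseline impulsivity and treatment group". The SAP gives no reason for the difference.

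Two Protocol statements bear on the point. Under Randomization Procedures: "Eligible ADHD participants will be randomized to treatment with LDX or GXR using a 1:1 ratio". Under Follow Up Evaluation and MRI Scan: "we will repeat all diagnostic assessments with the exception of the diagnostic interview". So scores exist at both times.

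**The concern.** A change score usually remains correlated with its own baseline. If the baseline is left out of the model, that variation stays in the residual and the interaction is estimated less precisely than it could be.

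The interaction carries the Secondary Objective: whether baseline imaging tells which drug a child will respond to. Interaction tests in a trial of this size have limited power, so precision given away matters more here than it would for a well-powered main effect. The covariate is already in the data set, because no change score can be formed without it.

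**Working it through.** **Inputs from the documents.** n=60, f²=0.09, two-sided 5% and 80% power (SAP, Secondary Objective). The Protocol's Description of Subject Population gives 30 for ADHD under "Number of completers required to accomplish study aims", so n=30 is shown as well.

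**Assumed inputs.** The documents give neither the pre-post correlation of impulsivity (ρ) nor the post/pre SD ratio (k). I take ρ from 0.3 to 0.9 and k=1, then vary k from 0.8 to 1.3. ROIs are first taken as uncorrelated with baseline impulsivity. The number of interactions is not stated; I use u=1, and u=2 for one measure per named circuit.

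**The plan's own figure.** The model has an intercept, Group, u ROIs and u interactions, so error df v = n − 2 − 2u. Power is from the noncentral F with λ = n·f² = 60 × 0.09 = 5.4. For u=1, v=56, this gives 62.7%, not 80%. At 80% power the minimum detectable f² is 0.135 (u=1) or 0.170 (u=2). I do not reproduce 0.09, so the gain is worked out from both starting points.

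**Effect of adjustment.** Adjusting a change score for its baseline multiplies residual variance by

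m = k²(1−ρ²)/(1+k²−2ρk) = 1 − (1−ρk)²/(1+k²−2ρk).

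Thus m ≤ 1, with equality only when ρk=1. At k=1, m=(1+ρ)/2. The adjusted effect size is f²/m, with v reduced by 1. For ρ=0.3, m=0.65 and f²/m = 0.09/0.65 = 0.138.

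Power at f²=0.09, k=1:

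| n | u | unadjusted | ρ=0.9 | ρ=0.7 | ρ=0.5 | ρ=0.3 |
|---|---|---|---|---|---|---|
| 60 | 1 | 62.7% | 64.9% | 69.7% | 75.1% | 80.8% |
| 60 | 2 | 51.3% | 53.5% | 58.4% | 64.2% | 70.9% |
| 30 | 1 | 35.3% | 36.8% | 40.3% | 44.6% | 50.0% |
| 30 | 2 | 26.2% | 27.3% | 30.1% | 33.7% | 38.3% |

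At n=60 the gain is 2.2 to 18.1 points (u=1) and 2.2 to 19.6 points (u=2).

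**From an 80% start.** With f² set so that the unadjusted model has 80% power at n=60 (0.135 or 0.170), the gain is 1.9 to 13.5 points (u=1) and 2.1 to 14.1 (u=2).

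**ROIs correlated with baseline impulsivity.** The ROI main effects then already absorb part of what the covariate would explain. Let each ROI correlate c with baseline impulsivity, let the ROIs be mutually uncorrelated, and let them relate to the post score only through baseline. With k=1 the unadjusted residual variance is 2(1−ρ) − u(1−ρ)²c² and the adjusted one is 1−ρ², so m = (1+ρ)/(2−(1−ρ)uc²). At n=60 and f²=0.09:

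- c=0.3: gain 2.0 to 16.9 points (u=1), 1.8 to 16.6 (u=2).
- c=0.5: gain 1.6 to 14.5 points (u=1), 1.1 to 10.6 (u=2). For u=1, ρ=0.3: m = 1.3/(2 − 0.7×0.25) = 0.712.

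**Unequal variances.** Over ρ 0.3 to 0.9 and k 0.8 to 1.3, with c=0, n=60 and f²=0.09, the largest gain is 27.0 points (u=1) or 30.9 (u=2), at ρ=0.3, k=0.8. The smallest is where ρk=1 (for example ρ=0.8, k=1.25): nothing is gained and the lost degree of freedom costs 0.03 points (u=1) or 0.05 (u=2). At n=30 that cost is 0.09 or 0.12 points.

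**Validity check.** In simulations with no interaction (4,000 runs per case, n=30 and 60, ROI-baseline correlation 0.3), the interaction F test rejected in 4.7% to 5.3% of runs unadjusted and 4.4% to 5.7% adjusted. Simulated power at n=60, u=1, k=1, c=0 rose from 59% to 76% at ρ=0.3 and from 61% to 62% at ρ=0.9, in line with the formula.

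**The case against.** The strongest defence is that the two models need not share a covariate set. In path b the predictor is circuit change after randomisation. It is not itself randomised, so baseline impulsivity can confound it and adjustment protects against bias. In the moderation model Group is randomised and that reason falls away. This stands: the contrast with path b shows that the covariate is available and already in use, not that the moderation model is wrong.

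A second defence is that the size of the benefit cannot be read from the documents. That also stands. The trial's premise links these circuits to impulsivity, so ROIs uncorrelated with baseline impulsivity is the favourable case, and the upper ends at c=0 should be read that way. The direction hardly depends on this: across the cases examined, the worst outcome is a trivial loss.

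Three stronger readings are tempting, and the documents do not support them:

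- A reader might infer that the omission biases or invalidates the moderation test. Randomisation rules out that bias in the interaction, and the unadjusted test holds its size.
- A reader might infer that the covariate would secure the stated 80% power. It reaches about 81% at f²=0.09 only for one interaction under the favourable end of the assumptions (ρ=0.3, c=0, k=1), and at n=30 with k=1 it does not exceed 50%.
- A reader might infer that the likelihood ratio test rejects too often in a sample this small. The SAP names no reference distribution, and in a normal linear model the statistic is a monotone function of the partial F, so it can be referred to an exact distribution.

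**Conclusion.** The point holds as a precision loss in a secondary analysis. At n=60, equal variances and ρ from 0.9 to 0.3, the gain forgone is about 2 to 18 power points for one interaction and 2 to 20 for two, provided f²=0.09 and the ROIs are uncorrelated with baseline impulsivity. The figure does depend on the starting power. It also shrinks as the ROIs become more correlated with baseline impulsivity, and nearly disappears when ρ times the SD ratio is close to 1, where the loss stays below 0.1 point at n=60. The range is therefore conditional, not an estimate for this trial. It is a modest free improvement. The unreproduced f² and the gap between 60 and 30 children are separate matters that this change does not resolve.

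**What to change.** In the SAP's Secondary Objective, add to each moderation model the baseline value of the same impulsivity measure whose change is the outcome. Write this in before the outcome data are analysed, so that the covariate cannot look chosen after the fact.

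The cost is one sentence in the SAP and one degree of freedom per model. No new data, visits or instruments are needed.

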Healthy control participants and participants with possible ADHD may be recruited from Protocol #7549 into this protocol. To minimize participant burden, we may share de-identified data collected under Protocol #7549 with this protocol, and vice versa. For example, we may share information collected as part of the lifetime diagnostic interview between the two protocols so that participants do not need to repeat this lengthy assessment and can instead provide an update on their mental health. Otherwise, assessment and MRI scanning procedures differ between this protocol and Protocol #7549; therefore healthy control participants will be assessed and scanned separately for each of these protocols.

Inclusion/Exclusion Criteria

Name the subject group/sub sample

Children with ADHD

Create or insert table to describe the inclusion criteria and methods to ascertain them

ADHD Participants	Methods of Ascertainment
1. The participant satisfies DSM-5 criteria for a primary diagnosis of ADHD, any subtype.	1. K-SADS administered by research staff (BA level or higher).
2. Participants must provide assent and a legal guardian must provide consent.	Interview, Staff Doctors
3. The participant is male or female 6 - 17 years of age and in good physical health.	Interview, Staff Doctors
4. Girls of childbearing potential must have a negative urine pregnancy test and must be using adequate contraception.	Urine pregnancy test performed by Study Staff; Interview, Staff Doctors
5. English Speaking.	Telephone Screening Questionnaire

Create or insert table to describe the exclusion criteria and methods to ascertain them

ADHD Participants	Methods of Ascertainment
1. The potential participant has a comorbid Axis I psychiatric diagnosis or other symptomatic manifestations that, in the opinion of the examining physician, will contraindicate LDX or GXR treatment or confound safety assessments.	Medical history by Staff Doctors
2. The potential participant meets DSM-5 criteria for active substance abuse and/or dependence.	K-SADS, interview by Staff Doctor
3. The potential participant is currently taking, or has taken within the past 4 months, a psychotropic medication.	Medical history by Staff Doctors
4. The potential participant has a documented allergy or intolerance to LDX or GXR products.	Medical history by Staff Doctors

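### The moderation model has no age or Group x age term in a sample aged 6-17, so a significant Group x ROI result could not be attributed to the circuit rather than to age

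*SAP*

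**What the plan says.** The SAP, Secondary Objective, uses "linear regression models with pre-post change scores in impulsivity measures as outcomes". The predictors are Group and "baseline measures of cognitive control and reward processing circuits measured in predefined regions of interest (ROIs), and their interactions as predictors". For several imaging measures together, "Likelihood ratio tests will be used to test the effect of moderation with combination of multiple brain imaging measures". The power paragraph gives a minimum detectable "f^2 is 0.09 (smaller than medium effect size 0.15") at n=60, "with 80% power for a two-sided test at the 5% significance level". No model anywhere in the SAP has an age term. The only covariates it names, in path b of the mediation analysis, are baseline impulsivity and treatment group.

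On age and weight, the protocol says the following.

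- ADHD inclusion criterion 3: "The participant is male or female 6 - 17 years of age and in good physical health".
- Titration of GXR: "For children under 25 kg/55 lbs, the dose of GXR will not exceed 1 mg per day"; otherwise the range is 1-4 mg. The rule is repeated under procedures for minimizing risks.
- Titration of LDX: 20-70 mg, with no weight rule.
- Randomization Procedures: 1:1, with no stratification by age or weight stated.
- Description of subject population: "Healthy control children, who will be matched on age and sex". These controls do not enter the moderation model.

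**The concern.** Randomization balances age between the arms. It does not settle which of two correlated baseline variables carries an interaction with treatment. If the drugs work differently in younger and older children, and an ROI measure changes with age, a model that omits Group x age lets Group x ROI absorb that difference.

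The protocol gives one reason not to rule out a drug-by-age difference: the lightest children, mostly the youngest, have a lower dose ceiling in one arm only. That is used here purely as a feature of the design; no dose rule is judged.

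The secondary hypothesis is that a child's pattern of circuit anomalies indicates which drug will work. As modelled, a finding that children with one kind of reward-circuit signal respond less to GXR could not be told apart from a finding that younger children respond less to GXR.

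**Working it through.** **The plan's own figure.** The SAP states a minimum detectable f² of 0.09 at n=60. With the F test for one added interaction in a three-predictor model (noncentrality f² x N, 56 residual df), the two-sided 5% value for 80% power is 0.135, and power at f²=0.09 is 63%. The stated figure does not reproduce. That is a separate matter, and nothing below rests on it. The values 0.09 and 0.15 are borrowed only as convenient sizes for an assumed drug-by-age effect; the SAP uses them for Group x ROI.

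**Inputs.**

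- From the documents: the model terms, 1:1 allocation, ages 6-17, two-sided 5%, n=60 (SAP) and 30 children with ADHD (protocol Lay Summary).
- Assumed: ROI-age correlation ρ of 0.3, 0.5 or 0.7; a linear drug-by-age effect of f² 0.09 or 0.15; age uniform over 6-17; no true Group x ROI effect.

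**Why the test rejects too often.** With age and ROI standardized, a true Group x age effect of size f² appears in the model without age as a Group x ROI effect of about

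f²(apparent) = ρ²f² / [1 + (1 − ρ²)f²].

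For ρ=0.5 and f²=0.15: 0.25 x 0.15 / (1 + 0.75 x 0.15) = 0.0375 / 1.1125 = 0.034. At n=60 the noncentrality is 60 x 0.0337 = 2.02, so the test rejects about 29% of the time. Simulation, which lets the sample correlation vary, gives 27%.

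**Simulated false-positive rate for Group x ROI** (one ROI, F test, 20,000 trials per cell):

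| n | Drug-by-age f² | ρ=0.3 | ρ=0.5 | ρ=0.7 |
|---|---|---|---|---|
| 60 | 0.09 | 9.7% | 18.7% | 33.3% |
| 60 | 0.15 | 12.9% | 27.1% | 48.7% |
| 30 | 0.09 | 7.0% | 11.5% | 17.2% |
| 30 | 0.15 | 8.2% | 14.6% | 25.5% |

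If ρ or the drug-by-age effect is zero, the rate is about 5%. Adding age as a main effect alone changes nothing (n=60, f²=0.09: 9.9%, 18.6%, 33.3%). Adding age and Group x age returns every cell to about 5%.

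**Weight cap as the only source.** Assume 10-25% of children fall under the cap and that their response to GXR is 0.5-1.0 SD worse. At n=60 the rate runs from 5.1% (10% capped, 0.5 SD, ρ=0.3) to 13.0% (25% capped, 1.0 SD, ρ=0.7). With age and Group x age added it is again about 5%.

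**Cost in power.** For a true Group x ROI effect of f²=0.15 and no drug-by-age effect:

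| n | Model as stated | + age, Group x age: ρ=0.3 | ρ=0.5 | ρ=0.7 |
|---|---|---|---|---|
| 60 | about 80% | about 75% | about 67% | about 53% |
| 30 | about 47% | about 41% | about 35% | about 25% |

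The one-term minimum detectable f² at n=60 rises roughly as 0.135 / (1 − ρ²): 0.135/0.91 = 0.15, 0.135/0.75 = 0.18 and 0.135/0.51 = 0.26.

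**The case against.** The strongest reply is that both inputs behind the large figures lie outside the documents. Neither the ROI-age correlation nor any drug-by-age effect on response is given, and matching controls on age is ordinary practice that does not show these ROIs to be strongly age-dependent. That stands, and it is why the size is given as a range that starts at 5%.

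Three stronger readings are tempting and not supported.

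- A reader might infer that the weight cap itself builds in a drug-by-age difference in response and so produces rates of 27% or 49%. The cap fixes a dose ceiling. A worse response under it is an inference, since the protocol titrates to the lowest dose that achieves response, and the share of children under 25 kg is not stated. The cap alone gives about 5-13%; the larger figures need a drug-by-age slope across the whole age range.
- A reader might infer that ROI values enter unadjusted for age. The SAP does not say whether they are raw, scaled or age-normed.
- A reader might infer that a false MRI marker would reach the clinic. This is a secondary objective of a small mechanism study whose protocol aims only to explore predictors of response.

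It is also fair that age is one of several correlated baseline variables, and that adjustment costs most power exactly where it removes most error. That argues for reporting both models, not for omitting age.

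**Conclusion.** The concern holds in limited form. The stated model cannot separate moderation by a circuit from moderation by age, so a significant Group x ROI term would not by itself support the secondary hypothesis. This follows from the model and the age range.

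How often it would mislead is not known. Under the assumed linear drug-by-age effect (f² 0.09-0.15) and ROI-age correlation (0.3-0.7), the false-positive rate is about 10-49% at n=60 and 7-26% at n=30. With the weight cap as the only source it is about 5-13% at n=60. If either ingredient is absent there is no inflation. The change is worth making because age is already recorded and the remedy is specific, but the documents do not show that the bias is present.

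**What to change.** In the SAP's Secondary Objective, prespecify a second moderation model with age and Group x age added. Report it beside the model as stated. Attribute moderation to a circuit only if the Group x ROI terms hold in the age-adjusted model; otherwise report that circuit and age could not be separated. An age main effect alone is not enough. State also whether ROI measures are entered as measured or age-normed.

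Scoring ROIs as deviations from age-expected control values is a useful supplement, because the objective defines anomalies against healthy controls. It is not equivalent: the protocol gives ten controls in the Lay Summary and 30 completers under Description of Subject Population, and norms over ages 6-17 from so few would be imprecise.

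The cost is SAP wording, two degrees of freedom and the power loss shown in the working, which the SAP should state. No new data are needed.
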